## STUDY SCHEMA

This is a prospective, phase Ib/II study of the preoperative combination of pembrolizumab (pembro) and radiation therapy (RT) in patients with operable breast cancer. Patients with newly diagnosed, Stage I-III breast cancer who are planned for breast-conserving surgery and adjuvant whole breast radiation therapy will be recruited into one of 2 cohorts as per their biomarker profile as depicted below. The TNBC cohort will have 50 subjects (10 TNBC subjects for phase Ib and 40 TNBC subjects for phase II) and the HR+ cohort will have 10 subjects. Enrollment will start with the phase Ib TNBC cohort. The trial will be conducted in a Bayesian design, wherein safety as assessed by lack of delay in standard of care treatment will be assessed after 3, 6, and 9 patients have initiated standard of care treatment in each cohort. Standard of care treatment is defined as breast-conserving surgery or initiation of neoadjuvant systemic chemotherapy. If the phase Ib TNBC trial meets a pre-specified safety endpoint, enrollment in

the phase II TNBC trial and HR+ cohort will take place.

Study treatment will consist of 2 doses of neoadjuvant pembro. The second dose will be given in combination with a RT boost. The primary objectives are: 1) to assess the feasibility of the preoperative combination of pembro and RT as defined by the number of patients who do not necessitate a delay in standard of care treatment, 2) to assess the change in tumor infiltrating lymphocyte (TIL) score with therapy. The secondary objectives are to describe the toxicity with preoperative pembro and RT up to 15 weeks after administration of pembrolizumab, to assess the invasive disease-free (iDFS) survival, and to assess the pathological complete response (pCR) rates.

- The first dose of pembro will be given on cycle 1, day 1 (C1D1). Each cycle will be 21 days. The second of pembro dose will be given on C2D1 (+/- 3 days).
- RT will be administered concurrently within one week of the second dose of pembro (C2D1 + 5 calendar days). 8Gy will be delivered in 3 fractions over 3 to 5 business days (for a total dose of 24Gy).
- Standard of care treatment, including breast-conserving surgery or additional neoadjuvant systemic therapy, will be pre-set to start 8 weeks after study enrollment (+/- 5 days).
- Research blood and stool will be obtained after consent up to C1D1. It will also be obtained on C2D1 (+/- 3 days) and at the time of initiation of standard of care treatment (+/- 5 days).

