- Research tumor biopsy will be performed after consent up to C1D1 (in the HR+ cohort, a diagnostic biopsy accepted if sufficient archived tissue is available) and on C2D1 (+/- 3 days) prior to the initiation of radiation therapy. Biopsies will be processed for scSeq and tumor infiltrating

- lymphocytes (TIL) analysis.
- Research tissue will also be obtained prior to the initiation of standard of care treatment at week 7 (+/- 5 days). If standard of care treatment consists of surgery, surgical tissue will be used. If it consists of further neoadjuvant systemic therapy, another research biopsy will be conducted. Fresh tissue may also be procured at the time of surgery if the surgery occurs after completion of neoadjuvant systemic therapy. This will be determined at the discretion of the treating physician.

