Further, there is a growing body of evidence indicating that women with breast cancers of certain subtypes are ideally suited for immunotherapy trials. Specifically, dense lymphocytic infiltration has been observed in a significant proportion of TNBCs and HER2-enriched tumors, indicating an inherent interplay between the tumor and the immune system. Although HR+/HER2- tumors are less likely to be infiltrated by CD8+ cytotoxic T-cells compared to TNBCs and HER2+ tumors, approximately 40% of these tumors do display a CD8+ infiltrate. It has been suggested that expression of the estrogen receptor results in decreased immunogenicity. Thus, it is likely that the subset of HR+/HER2- tumors that display increased lymphocytic infiltration are not as strongly driven by estrogen and belong to the Luminal B subtype. Thus, this study focuses on the immunogenicity of high-risk breast cancer subtypes that are likely to display a dense lymphocytic infiltration including TNBC and HR+/HER2- tumors that are more likely to be consistent with Luminal B subtypes, defined by 2 out of 3 of the following characteristics: grade II-III, Ki-67 > 20%, ER < 75%.

Locoregional therapies for patients with breast cancer consist of either mastectomy or lumpectomy followed by whole breast radiation therapy (WBRT). Both have been shown to be equivalent to mastectomy in terms of local control and overall survival. Recently, radiation therapy (RT) has been described to have numerous immune-modulatory effects. RT-induced tumor cell death increases the supply of tumor-specific antigens, leading to the release of signaling molecules that attract immune cells to the tumor microenvironment and to the upregulation of programmed death-ligand 1 (PD-L1) on tumor cells. Whether or not RT combined with PD-L1 blockade synergistically increases the tumor immunogenicity, compared to PD-L1 blockade alone, is the subject of this trial. Our study population will focus on women with immunogenic subtypes of breast cancer and/or those who are at high risk of recurrence. Our study design, which describes lead-in with administration of pembrolizumab alone prior to the addition of RT, will allow for examination of immune correlates in a staged fashion and subsequent determination the efficacy of our strategy.

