## 2.4 Endpoints

- **Primary Efficacy Endpoint: Feasibility**

Feasibility will be defined by the number of patients who do not necessitate a delay in standard of care treatment. Since the combination of pembrolizumab and RT has not been tested in the preoperative setting in patients with potentially curative disease, it is necessary to establish whether such preoperative treatment can be safely given without delaying curative-intent treatment.

- **Co-Primary Efficacy Endpoint: Change in TILs**

An increase in TILs is an indicator of immune system engagement. A lead in with pembrolizumab alone followed by the combination of pembrolizumab with RT will allow for serial assessment of TILs. This will establish the contribution of RT to the immune response generated by pembrolizumab.

- **Safety Evaluations**

Immune related adverse events that result from checkpoint blockade can occur weeks after the drugs are administered. Therefore, adverse events will be recorded up to 15 weeks after administration of pembrolizumab and radiation therapy and graded according to CTCAE, Version 4.03. Immune related adverse events will also be documented for up to 1-year post treatment. When considering if an adverse event is immune related, a general principle is that differential diagnoses should be diligently evaluated according to standard medical practice. Non-inflammatory etiologies should be considered.

- **iDFS**

iDFS will be defined as the time from completion of surgery to the first occurrence of the following events: invasive ipsilateral, local, regional, or distant recurrence, or death due to breast cancer.

- **pCR**

pCR will be defined as the absence of invasive disease in the breast and lymph nodes at the time of curative-intent surgery.

---

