#### ***Study Population***

Subjects with pathologically confirmed, localized (Stage I-III) breast cancer with a primary tumor size of at least 2cm for whom breast-conserving surgery and adjuvant whole breast RT is planned will be recruited into one of 2 cohorts, delineated by breast cancer subtype (TNBC or HR+). We anticipate that a low proportion of patients who are planning breast-conserving surgery may ultimately choose mastectomy. The receipt of a pre-operative boost should not preclude the ability to receive mastectomy with immediate reconstruction. The outcomes of these patients will be captured and followed on protocol.

The magnitude of TILs is reported to be higher in TNBC tumors than HR+/HER2- tumors. It is postulated that TNBCs have a higher lymphocytic infiltrate due to higher mutational load, which enhances immunogenicity and results in increased TIL recruiting. Clinical data with checkpoint blockade therapy supports the increased immunogenicity of TNBC and HER2+ tumors compared to HR+/HER2- tumors. For example, the Phase Ib JAVELIN study reported an ORR of 8.6%, 3.8%, and 2.8% in TNBC, HER2+, and ER+ or PR+/HER2- subtypes, respectively. Due to the differences in intrinsic risk and baseline immunogenicity, the cohorts in this study are delineated by biomarker subtype.

As such, the cohorts include:

- 1) Cohort 1: TNBC patients with primary tumors measuring at least 2 cm
- 2) Cohort 2: High-risk, ER-positive and HER2-negative breast cancer patients with primary tumors measuring at least 2 cm

ER-positive and HER2-negative breast cancer will be defined by ER expression  $\geq 10\%$  by immunohistochemistry (IHC) and HER2-negativity per ASCO-CAP guidelines. High-risk disease will be defined by the presence of at least 2 of the following 3 criteria: histologic grade II-III, Ki-67  $> 20\%$ , ER expression  $< 75\%$  by IHC. TNBC will be defined by ER and PR expression  $< 10\%$  by IHC and HER2-negativity by ASCO-CAP guidelines.

It is well known that systemic therapy activates the immune system. Therefore, clear, discriminate assessment of the contribution of RT to tumor immunogenicity in each of the 2 subsets requires that this trial be conducted in the absence of prior therapy. We recognize the

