#### 5.1.2 RT Boost

The Gross Target Volume (GTV) for the boost will be defined by preoperative imaging +/- clips placed into the tumor at the time of the biopsy. A planning target volume (PTV) will be created from the GTV as per departmental partial breast irradiation treatment planning guidelines. The PTV will be treated with 8 Gy x 3 fractions (24 Gy total) with external beam techniques. RT will

begin within 5 calendar days of the second dose of pembrolizumab.

A total dose of 24 Gy will be delivered over 3 fractions within a 3 to 5-day period. Doses of 8 Gy will be given once daily for 3 treatment days.

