**MerFISH:** In conjunction with [name] (Biomedical Sciences, Cedars-Sinai), frozen tumor samples will be submitted for copy number and spatial assessment of thousands of different RNA species in single cells using fluorescence in situ hybridization (FISH). The eventual goal of this technology is to build a 3-D model of the tumor microenvironment with data on expression levels of various RNAs in tumor, stroma, and immune infiltrate. Changes in gene expression levels through the course of therapy will allow for the identification of drivers of safety and response.

**Single-cell RNA Sequencing:** In collaboration with [name], correlative endpoints have been designed to establish the immunogenic contribution of RT to checkpoint blockade therapy

and define the molecular signatures that are associated with amplified tumor immunogenicity. Single cell gene expression profiling will be applied to research biopsies performed prior to pembrolizumab (in the TNBC cohort only) and in all cohorts, sequentially following administration of pembrolizumab and pembrolizumab + RT to identify tumors with an immunogenic response. For each biopsy, 10,000 live single cells will be isolated from the mixture using Fluorescence Activated Cell Sorting (FACS), disregarding cell type. These cells will be profiled individually using the 10X genomics single cell RNA-sequencing platform. The result of this processing will be a set of 10,000 gene expression signatures for each biopsy, where each profile informs on the type and molecular state of a single tumor cell.

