**Table 9.2.3 Stopping rules based on seven interim looks**

Number of Patients	Number to Continue	Probability to Stop	Cumulative Probability to Stop
3	2	0.008	0.008
6	3	0.013	0.021
9	4	0.010	0.031
12	5	0.007	0.038
15	6	0.005	0.044
18	7	0.004	0.047
20	8	0.009	0.048

**Table 9.2.4 Design operating characteristics under different scenarios for the true probability of  $P_d$  for TNBC cohort**

True Value of $P_d$	Probability to Stop	Expected N	Expected N given that we Stopped
0.10	0.003	19.96	6.48
0.30	0.233	17.76	10.38
0.50	0.834	11.01	9.28
0.60	0.967	8.11	7.70

The co-primary efficacy endpoint will be change in TILs. TILs will be assessed in paraffin embedded samples after the study is completed and will have no bearing on impact on continued enrollment for the trial. For each cohort, the mean percent change in TIL score before treatment and after pembrolizumab alone  $\mu_1$  will be compared to the mean change in TIL score before treatment and after pembrolizumab plus radiation  $\mu_2$  using the paired t-test or Wilcoxon sign test depending on the distribution of the data. A significance of 0.05 will be used to declare statistical significance. Let  $SD(\text{diff})$  be the standard deviation of the difference in percent change in TIL score before treatment and after pembrolizumab and before and after treatment with pembrolizumab and radiation. Data from 8 evaluable patients in the HR+ cohort achieve 80% power to detect an effect size of 1.16 using a two-sided paired t-test at the 0.05 level of significance. The effect size is defined as the difference between the two means divided by  $SD(\text{diff})$ ,  $(\mu_1 - \mu_2) / SD(\text{diff})$ . This is equivalent to an absolute difference of 20% between the mean change in TIL scores assuming an  $SD(\text{diff})$  of 17%. For the TNBC cohort, assuming 16 patients are evaluable, the effect size that is detectable with the same power and type I error is 0.75.

Comparisons of clinical characteristics among cohorts will be conducted using descriptive summary statistics using median and range. Changes in TIL score will be compared between cohorts using Fishers exact test.

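### The co-primary TIL comparison cannot establish the contribution of RT, because RT, the second pembrolizumab dose and about three more weeks all fall between the two samples compared

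*Combined protocol and SAP*

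**What the plan says.** Change in TILs is a co-primary endpoint. Section 2.4 describes a pembrolizumab lead-in followed by pembrolizumab with RT, and states the result in advance: "This will establish the contribution of RT to the immune response generated by pembrolizumab". Two other places use similar wording. Section 3.0 (Study Population) speaks of "clear, discriminate assessment of the contribution of RT to tumor immunogenicity in each of the 2 subsets", and the single-cell RNA sequencing text in Section 8.1 says the correlative endpoints were designed to "establish the immunogenic contribution of RT to checkpoint blockade therapy". Section 1.1 frames the trial's question the same way: "Whether or not RT combined with PD-L1 blockade synergistically increases the tumor immunogenicity, compared to PD-L1 blockade alone, is the subject of this trial".

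The sequence of treatment and sampling is as follows.

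- Baseline tissue is taken before C1D1. In the HR+ cohort it may be the archived diagnostic biopsy.
- The next biopsy is "on C2D1 (+/- 3 days) prior to the initiation of radiation therapy" (Study Schema).
- Of pembrolizumab, the Schema says: "The second dose will be given in combination with a RT boost". Section 5.1.2 has RT "begin within 5 calendar days of the second dose of pembrolizumab".
- The last tissue is taken at Week 7, when standard of care starts. Section 6.4, footnote 3, puts this three weeks after the second dose. Surgical tissue is used if standard of care is surgery; otherwise another biopsy is taken.

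Section 9.2.1 compares the mean percent change from baseline after pembrolizumab alone with "the mean change in TIL score before treatment and after pembrolizumab plus radiation", using a paired t-test or Wilcoxon test at 0.05. Section 5.3 states that there is no randomization, and the Study Summary lists no reference therapy.

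**The concern.** A within-patient sequence attributes a change to one component only if that component is all that differs between the two samples. Here at least three things differ: RT, the second pembrolizumab dose and elapsed time. In patients who go straight to surgery, the specimen type differs as well.

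The protocol's own text makes a non-RT change plausible. Section 1.5 describes a long half-life and target engagement lasting beyond 21 days, so the first dose may still be acting after C2D1. Appendix B, item 7, says that no validated method exists for scoring TILs after neoadjuvant treatment.

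At stake is what a positive co-primary result would mean. As worded, a significant test would be reported as an RT effect, although the same result could arise with no RT effect at all.

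**Working it through.** **1. The plan's own figures.** Inputs from Section 9.2.1: two-sided 0.05, paired t-test; HR+ n = 8, effect size 1.16; TNBC n = 16, effect size 0.75; a 20% difference with SD(diff) 17%. Power comes from the noncentral t with n − 1 degrees of freedom and noncentrality (effect size) × √n.

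- n = 8: 1.16 × √8 = 3.28, power 0.803.
- n = 16: 0.75 × √16 = 3.00, power 0.801.
- 20/17 = 1.176 at n = 8: power 0.813.

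The stated 80% is reproduced. No number in the plan is wrong; the question is what the power is for.

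**2. What is tested.** Write B, W4 and W7 for the TIL score at baseline, C2D1 and Week 7.

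- Absolute scale: (W7 − B) − (W4 − B) = W7 − W4.
- Relative scale, if percent change means that: (W7 − B)/B − (W4 − B)/B = (W7 − W4)/B.

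Baseline cancels on the first scale and remains as a divisor on the second. Either way the test compares Week 7 with Week 4. On the absolute scale its mean is

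RT effect + second-dose effect + effect of about 3 more weeks (+ any core-to-surgical shift).

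With one treatment sequence and no group sampled without RT, only the sum can be estimated.

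**3. Illustration.** Assumptions, none of them from the documents: a true RT effect of zero, and a non-RT rise of 5 or 10 points between Week 4 and Week 7. SD(diff) = 17 is stated beside the HR+ calculation. Using it for n = 16 is a further assumption, because the plan gives only an effect size for TNBC. The same power formula applies, with effect size = rise/17.

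| Non-RT rise | Effect size | n = 8 | n = 16 |
|---|---|---|---|
| 0 | 0 | 5% | 5% |
| 5 points | 5/17 = 0.294 | 11% | 20% |
| 10 points | 10/17 = 0.588 | 30% | 60% |

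**4. Can the existing samples isolate RT?** The obvious candidate is (W7 − W4) − (W4 − B). It is zero under no RT effect only if pembrolizumab and time act equally over both intervals.

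- Plateau example: pembrolizumab adds 20 points by C2D1 and then holds. If RT adds a true 20, the contrast is 20 − 20 = 0. If RT adds nothing, it is 0 − 20 = −20.
- Precision: the contrast is W7 − 2·W4 + B. With equal, independent errors its variance is 1 + 4 + 1 = 6 units, against 2 for W7 − W4. The SD rises by √3, from 17 to 29.4. Power for 20 points at n = 8 falls from 81% to 38%.
- Intervals: archived HR+ tissue leaves the first interval unfixed.

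**The case against.** The strongest reply is one of scope. The formal objective (Section 2.1.2) is only to assess the change in TIL score with the combination. Section 9.2.1 labels the two changes by the treatment received and makes no claim about RT by itself. Section 1.1 poses a question. This is a single-arm pilot, and Section 9.2.1 says the TIL results do not affect enrollment. All of that is correct. It confines the fault to the claim in Section 2.4 and its echoes in Sections 3.0 and 8.1; the test and the objective stand. It does not rescue the claim. An early-phase design explains the absence of a control, but not the promise to establish a cause. Sections 2.4 and 9.2.1 nowhere acknowledge the second dose or elapsed time.

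Two partial safeguards deserve credit. Requiring no prior therapy (Section 3.0) removes a confounder, though a different one. Appendix B, item 4, excludes TILs at the previous core biopsy site, and the C2D1 sample also follows an earlier biopsy, so a biopsy effect is a weaker concern than the second dose and time.

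A reader might infer that the tabulated percentages are this trial's false-positive rates. They are not: the documents give no size for a non-RT shift, and with no shift the rate is the nominal 5%. A reader might also infer that the difference-of-changes contrast would isolate RT. Step 4 shows that it replaces one untestable assumption with another and loses more than half the power at n = 8.

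**Conclusion.** The concern holds as a fault in the stated conclusion. A significant paired test would support the statement that TILs changed further between Week 4 and Week 7 on a second pembrolizumab dose plus RT. It would not support attributing that change to RT. This follows from the schedule and the lack of any RT-free group, and needs no numerical assumption. The 11% to 60% range only shows how readily a modest non-RT rise could produce a positive test. It rests on an assumed zero RT effect, assumed rises of 5 or 10 points, and SD(diff) 17 in both cohorts.

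Two stronger readings are not supported. The documents do not show that RT adds nothing, or that a positive result would be mistaken; they show only that the causes cannot be told apart. Nor do they make the planned test invalid: as a before-and-after comparison it is legitimate, and its power figures are right for the combined change.

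**What to change.** In Section 2.4, and to match in Section 3.0 (Study Population) and Section 8.1 (single-cell RNA sequencing), replace the claim about RT's contribution with wording such as: *estimate the further change in TILs after the second pembrolizumab dose plus RT, relative to the post-lead-in sample; this cannot be separated from the second dose and elapsed time*. In Section 9.2.1, state that a significant result is to be interpreted only in that way.

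Keep the planned paired test. Do not add the difference-of-changes contrast as a test.

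The timing passages should also be reconciled, because they define the interval being tested. Standard of care is placed at Week 7 or three weeks after the second dose in some places, and at 8 weeks after enrollment or trial initiation in others (Study Schema, Section 3.0, Section 6.4).

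The cost is a weaker stated conclusion. No patients, samples or treatments change. Attribution to RT would need a concurrent group sampled at the same times without RT, which this design does not have.

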### 3.0 STUDY DESIGN

#### ***Study Design***

This is a prospective, single-institution, Phase Ib/II study of the preoperative combination of pembrolizumab (pembro) and radiation therapy (RT) in patients with operable breast cancer (TNBC). The two cohorts will consist of 50 TNBC and 10 HR+ women each. Enrollment will start with the Phase Ib TNBC safety cohort. The trial will be conducted in a Bayesian design, wherein safety as assessed by lack of delay in standard of care treatment will be assessed after 3, 6, and 10 patients have initiated standard of care treatment. If at least 80% of the first 10 subjects in the TNBC cohort proceed with standard of care therapy without delay, the combination will be deemed safe in the cohort, and enrollment in the HR+ cohort, as well as continued enrollment in the TNBC cohort (40 subjects), will occur at that time.

Each cohort will be evaluated for delay in curative-intent standard of care treatment every time 3 patients complete study therapy and undergo standard of care treatment. At each of those timepoints, if the posterior probability that a patient experiences a delay in standard of care treatment exceeds 20%, the cohort will stop enrollment. In Bayesian statistics, the posterior probability of a random event or an uncertain proposition is the conditional probability that is assigned after the relevant evidence or background is taken into account. This design will assure that a cohort does not continue enrollment if early delays in standard of care treatment are seen. Enrollment will be carried out continuously and will not be stopped in order to evaluate the posterior probability of a delay. However, the number of patients undergoing assessment for a possible delay simultaneously will not exceed four in each of the 2 cohorts.

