## **9.0 STATISTICAL CONSIDERATIONS**

### **9.1 Sample Size**

#### **Phase Ib:**

It is imperative that any experimental pre-operative therapeutic innovation not undermine the timing of curative-intent treatment in localized breast cancer, the primary endpoint for the Phase Ib study is safety/tolerability, as defined by the number of patients who do not necessitate a delay in standard of care treatment (breast surgery or neoadjuvant systemic therapy followed by breast surgery). A small number of patients of TNBC will be included in this cohort to establish safety of the regimen as described below for consideration for further study. Along with safety, assessment of TILs through the course of treatment in this cohort will establish the immunogenicity of this combination. If at least 80% of the first 10 subjects in the TNBC cohort proceed with standard of care therapy without delay, the combination will be deemed safe in the cohort, and enrollment in the HR+ cohort (10 subjects) will occur at that time.

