## 9.2 Data Sets Analyzed

### Data Analyses/Study Endpoints

#### 9.2.1 Efficacy Analysis

The primary analysis will be based on an intention-to-treat approach and will include all subjects who receive a dose of study drug.

Phase Ib:

The primary efficacy endpoint will be feasibility as defined by the number of patients who do not necessitate a delay in standard of care treatment. Let  $P_d$  be the true probability that a patient experiences a delay. The trial will stop if there is statistical evidence that  $P_d$  exceeds 20%. We will use a Bayesian sequential design by checking whether  $P_d$  exceeds this threshold value after 3, 6, 9, ... patients are evaluable for feasibility. The decision rule is to stop the trial if the posterior probability that  $P_d$  exceeds 0.20 is 0.95 or more;  $P(P_d > 0.2 | \text{data}) > 0.95$ . A non-informative prior distribution for  $P_d$  will be used. Table 9.2.1 gives the stopping rules for the design at each look and column 2 gives the maximum number of patients with delay in order for the trial to proceed. Stopping rules will also apply for any patients with clinical progression of disease during study treatment, although this is expected to be uncommon. For example, if 4 or more delays in treatment are observed after enrolling 6 patients, the trial stops. The third column gives the probability of stopping the trial when in fact, the true  $P_d = 0.20$ . This is the equivalent of the Bayesian type I error probability. The target type I error probability was set at 0.05.

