**Table 9.2.1 Stopping rules based on four interim looks**

Number of Patients	Number to Continue	Probability to Stop	Cumulative Probability to Stop
3	2	0.008	0.008
6	3	0.013	0.021
9	4	0.010	0.031
10	4	0.011	0.042

Number to continue is the maximum number of delays in standard of care treatment for not stopping the trial.

Table 9.2.2 gives the design operating characteristics under selected values of the true probability  $P_d$  for the HR+ cohort. It gives the probability of stopping the trial under the alternative hypothesis, the expected sample size, and the average sample size given that the trial stopped. For example, if the true value of  $P_d$  is 0.5, then there is an 64% chance that the trial is stopped early and the average sample size is about 8. On the other hand, there is a small chance of stopping the trial if  $P_d$  is small; 0.3% chance of stopping the trial when in fact  $P_d = 0.1$ . Tables 9.2.3 and 9.2.4 list the same operating characteristics for the TNBC cohort.

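### The plan does not say how the at-most-2-delays gate for the first 10 TNBC patients ranks against the looser stopping limits in Section 9.2.1, and the TNBC operating characteristics leave the gate out

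*Combined protocol and SAP*

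**What the plan says.** **Go rule.** Section 3.0 (Study Design) sets the condition "If at least 80% of the first 10 subjects in the TNBC cohort proceed with standard of care therapy without delay". If it is met, the combination is deemed safe and the HR+ cohort opens, "as well as continued enrollment in the TNBC cohort (40 subjects), will occur at that time". Section 9.1 (Phase Ib) repeats the 80% condition and its consequence: "the combination will be deemed safe in the cohort, and enrollment in the HR+ cohort (10 subjects) will occur at that time".

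**Stopping rule.** Section 9.2.1, also under Phase Ib, works from evidence of excess delay: "The decision rule is to stop the trial if the posterior probability that" Pd exceeds 0.20 is at least 0.95, where Pd is the true probability of a delay. It says of the stopping table that "column 2 gives the maximum number of patients with delay in order for the trial to proceed". The note under Table 9.2.1 puts it slightly differently: "Number to continue is the maximum number of delays in standard of care treatment for not stopping the trial".

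**Printed limits (maximum delays to continue).**
- Table 9.2.1: 2 at 3 patients, 3 at 6, 4 at 9, 4 at 10. It follows the Phase Ib text, but the companion Table 9.2.2 is introduced as the HR+ operating characteristics.
- Table 9.2.3, assigned to TNBC: 2 at 3, 3 at 6, 4 at 9, 5 at 12, 6 at 15, 7 at 18, 8 at 20. It has no row at 10.

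Table 9.2.4 gives the matching TNBC operating characteristics.

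**The concern.** Feasibility is a primary endpoint, and the result in the first 10 TNBC patients decides whether 40 more TNBC and 10 HR+ patients are enrolled. With 3 or 4 delays in those 10, the go rule is not met, yet the tables put the cohort within the limit for continuing. The plan neither ranks the two rules nor describes this outcome, so the action would have to be settled after the data are known.

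The second issue is numerical. Every TNBC cohort that continues past patient 10 must first pass the 80% gate. If the TNBC tables were computed without it, they do not describe the design as written and understate how often the cohort fails to go forward.

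**Working it through.** **Inputs.** Go rule: 0.80 × 10 = 8 patients without delay, so at most 10 − 8 = 2 delays (Sections 3.0 and 9.1). Boundaries: as printed in Tables 9.2.1 and 9.2.3. Pd values: 0.20 is the threshold in Section 9.2.1; 0.10, 0.30 and 0.50 are scenarios in Tables 9.2.2 and 9.2.4.

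**Method.** Exact binomial recursion. Carry the probability f(k) of being unstopped with k delays from one look to the next; with m new patients, add f(k) × C(m,x) Pd^x (1−Pd)^(m−x) to the state k+x. The probability above the limit is the stopping probability at that look and is removed.

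**Step 1: reproduce the plan's figures, without the go rule.** At Pd 0.20 under Table 9.2.1:
- 3 patients: 0.2³ = 0.0080.
- 6 patients: stopping needs 4 or more delays. From 1 delay: 0.384 × 0.008 = 0.0031. From 2 delays: 0.096 × (3 × 0.04 × 0.8 + 0.008) = 0.096 × 0.104 = 0.0100. Sum 0.0131.
- 9 patients: 0.0101. 10 patients: 0.0113.
- Cumulative before rounding: 0.0424, printed 0.042.

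The same recursion gives 0.003, 0.171, 0.643 and 0.844 at Pd 0.10, 0.30, 0.50 and 0.60 (Table 9.2.2 prints 0.003, 0.17, 0.64, 0.84). The seven-look TNBC boundary gives a cumulative 0.048 at Pd 0.20 and 0.003, 0.233, 0.834 and 0.967 at the four scenarios, as printed in Tables 9.2.3 and 9.2.4. The stopping probabilities are therefore right for the boundaries alone, and they match only with the gate left out.

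**Step 2: add the gate.** P(3 or more delays in 10) = 1 − Σ(k=0 to 2) C(10,k) Pd^k (1−Pd)^(10−k). At Pd 0.20: 1 − (0.1074 + 0.2684 + 0.3020) = 0.3222. A path that crosses a boundary at 3, 6 or 9 patients already has at least 3 delays. So this is the whole probability of not proceeding by patient 10 when both rules apply.

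**Step 3: compare on the same horizon.** The undefined outcome (3 or more delays at 10, no boundary crossed) is the gate-failure probability minus the probability of having already stopped. At Pd 0.20 it is 0.3222 − 0.0424 = 0.2798 under Table 9.2.1 and 0.3222 − 0.0311 = 0.2911 under Table 9.2.3. The second is larger because Table 9.2.3 has no look at 10, so 5 delays there also goes unstopped.

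| | Pd 0.10 | 0.20 | 0.30 | 0.50 |
|---|---|---|---|---|
| Stopped by 10, Table 9.2.1 only | 0.003 | 0.042 | 0.171 | 0.643 |
| Not proceeding by 10, gate included | 0.070 | 0.322 | 0.617 | 0.945 |
| Undefined outcome, 4-of-10 limit | 0.067 | 0.280 | 0.447 | 0.303 |
| Undefined outcome, TNBC table | 0.068 | 0.291 | 0.491 | 0.408 |
| Stopped by 20, TNBC table as printed | 0.003 | 0.048 | 0.233 | 0.834 |
| Same table, gate inserted at 10 | 0.070 | 0.323 | 0.621 | 0.955 |

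On the 20-patient horizon, expected N falls from 19.96 to 19.29 at Pd 0.10 and from 17.76 to 13.37 at Pd 0.30.

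**Two small print points for the same recomputation.** The last row of Table 9.2.3 prints 0.009, but its cumulative column rises only from 0.047 to 0.048; the recursion gives 0.0009. Table 9.2.4 prints expected N 11.01 at Pd 0.50; the recursion gives 11.06. Neither affects the point.

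**The case against.** The best reply is that the rules do different jobs. The tables stop a cohort when there is strong evidence of excess delay; the 80% rule is a separate condition for expanding. Not crossing a harm boundary is not a finding of safety, and nothing in the documents says that staying within a table limit opens Phase II or the HR+ cohort. On that reading 3 or 4 delays means not stopped, but not expanded.

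Much of this stands. A reader might infer that the two rules flatly contradict each other; the documents do not support that, because both can be applied together. What remains is that no section states the layering, and the description of column 2 in Section 9.2.1 points the other way. Even with layering, the TNBC tables run past patient 10 without the gate.

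A reader might also take 4 of 10 as plainly a TNBC limit. The labelling does not settle this: Table 9.2.1 sits under Phase Ib, its companion is labelled HR+, and the TNBC table has no row at 10. The mismatch survives either way, because the TNBC table tolerates 4 delays at 9 and 5 at 12.

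Finally, it is tempting to set the 62% gate failure at Pd 0.30 against the printed 23%. That compares a 10-patient gate with stopping over 20 patients. The fair pairs are 0.617 against 0.171 by patient 10, or 0.621 against 0.233 over the full table.

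**Conclusion.** The point holds as one of undefined precedence and incomplete operating characteristics. The threshold that decides a primary endpoint and the opening of Phase II is not uniquely stated. The unaddressed outcome has probability 28% to 29% at Pd 0.20 and 45% to 49% at Pd 0.30, depending on which table applies. With the gate included, the probability of not proceeding at Pd 0.20 is 32%, where the printed cumulative stopping probability is 4.2% or 4.8% and the stated target is 0.05.

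These figures assume independent patients with a common Pd, the printed limits taken as given, and 10 evaluable patients at the gate. They do not depend on the prior, whose parameters the plan does not give.

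Two further inferences are not supported. The printed stopping probabilities are not miscalculated; they answer a narrower question than the design poses. And the documents do not say that these tables are what the monitoring committee is shown, so no claim about what it has been told can be made. Which delay limit is appropriate is for the sponsor and is not judged here.

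**What to change.** - Reconcile Sections 3.0, 9.1 and 9.2.1 so that one rule governs expansion after the first 10 TNBC patients, and state the action for 3 or more delays when no boundary has been crossed.
- If the 80% gate stands, say that the tables are harm-stopping boundaries that do not by themselves permit expansion, and reword the description of column 2 to match.
- Label the cohort to which Table 9.2.1 applies.
- Recompute the TNBC operating characteristics with the governing rule included and for the current cohort. Table 9.2.3 ends at 20 patients, while the TNBC cohort is now 10 + 40 = 50, so adding a row at 10 would not be enough.

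The cost is protocol and SAP wording plus recomputed TNBC tables. The downside is that, if the gate is kept, the stated chance of halting an acceptable regimen becomes less favourable: 0.070 instead of 0.003 at Pd 0.10 on the existing 20-patient table.
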